## Version History

*This Statistical Analysis Plan (SAP) is based on protocol version 5, dated 02 October 2024*

SAP Version	Date	Change(s)	Rationale
Final V1.0	19Oct2023	Not Applicable	Original Version
Final V2.0	19Feb2025	

1. Added required info to title page

2. Updated description to accommodate newly planned interim analysis and timing

3. Added the following sections that were not present in V1.0:

- Sample size calculation

- Handling of outliers

- p-value reporting and critical threshold

- Protocol deviations

4. Reduced number of correlations

5. Added details about derived variable calculations

6. Removed section on MRI Data Exclusion

7. Changed Bone Marrow Transplant (BMT) to Hematopoietic stem cell transplant (HSCT). BMT and HSCT are interchangeable terms for the purposes of this study and in comparison to the protocol and SAP V1.0

8. Updated the Analysis section to clarify differences from Protocol V5.0

9. Minor edits to clarify language and terminology throughout

10. Brief Assessment of Cognition (BAC) test has been removed from the SAP

11. Removed sensor-based gait and balance assessment

	Updated to incorporate FDA feedback, ICH E9 SAP guidelines, and newly planned use of Natural History Study (NHS) data in integrated analysis with a separate Phase 2 study (VGL101-01.201). Note that NHS Study Objective 3 is to use NHS as external control; the analysis planned here are consistent with that aim. The BAC was removed because vendor was unable to provide traceability of the derived variable calculation. The sensor-based gait and balance assessment was removed due to collection discontinuation (see study protocol).

Note: Author of Final V1.0 was [name]. Edits incorporated for v2.0 were done via collaboration of Vigil and Parexel study statisticians.

## List of Abbreviations and Definition of Terms

Abbreviation	Term
2MWT	2-Minute Walk Test
ADRG	Analysis Data Reviewer Guide
AE	Adverse Event
ALSP	Adult-onset Leukoencephalopathy with Axonal Spheroids and Pigmented Glia
ATC	Anatomical Therapeutic Chemical
BAC	Brief Assessment of Cognition
BMI	Body Mass Index
CBFS	Cortical Basal Ganglia Functional Scale
CBFS-M	CBFS – Motor
CBFS-NM	CBFS – Non-motor
CDISC	Clinical Data Interchange Standards Consortium
CDR ® +NACC-FTLD	Clinical Dementia Rating Scale plus National Alzheimer's Coordinating Center - Frontotemporal Lobar Degeneration
CDR ® +NACC FTLD-SB	CDR ® +NACC FTLD - Sum of Boxes
CGI-C	Clinical Global Impression - Change
CGI-S	Clinical Global Impression – Severity of Illness
COVID-19	Coronavirus Disease 2019
CRF	Case Report Form
CSF	Cerebrospinal Fluid
CSF1R	Colony-stimulating Factor 1 Receptor
CSR	Clinical Study Report
C-SSRS	Columbia-Suicide Severity Rating Scale
CV	Coefficient of Variation
CVA	Cerebrovascular Accident
eCRF	Electronic Case Report Form
EDC	Electronic Data Capture
EDL	Experiences in Daily Living
ET	Early Termination
FAQ	Functional Activities Questionnaire
GCP	Good Clinical Practice
GFAP	Glial Fibrillary Acidic Protein

Abbreviation	Term
HLT	High Level Term
HSCT	Hematopoietic Stem Cell Transplant
IA	Interim Analysis
ICF	Informed Consent Form
ICH	International Council for Harmonization
MedDRA	Medical Dictionary for Regulatory Activities
MMRM	Mixed Effects Model for Repeated Measures
MoCA	Montreal Cognitive Assessment
MRI	Magnetic Resonance Imaging
NfL	Neurofilament Light Chain
NHS	Natural History Study
NPI-12	Neuropsychiatric Inventory – 12 Item Version
PGI-C	Patient Global Impression - Change
PGI-S	Patient Global Impression – Severity of Illness
PT	Preferred Term
SAE	Serious Adverse Event
SAP	Statistical Analysis Plan
SD	Standard Deviation
SE	Standard Error
SOC	System Organ Class
sTREM2	Soluble Triggering Receptor Expressed on Myeloid Cells 2
TUG	Timed Up and Go
WHO	World Health Organization
WOCBP	Women of Child-bearing Potential
ZBI	Zarit Burden Interview

## 1 Introduction

This statistical analysis plan (SAP) describes the statistical analysis to be included in the Clinical Study Report (CSR) for the Protocol, “A Natural History Study of Patients with Adult-Onset Leukoencephalopathy with Axonal Spheroids and Pigmented Glia (ALSP)” (VGL101-01.002), known as the Illuminate study.

Background information is provided for the overall study design and objectives. Details regarding study conduct and data collection procedures are provided in the study protocol and corresponding case report forms (CRFs), which include comprehensive descriptions of the study design, methodologies, and data collection processes. This SAP references the latest version of the study protocol (Version 5.0). The SAP may contain modifications to the analysis plans as outlined in the protocol. In such cases, the SAP serves as the governing document for all analyses to be performed. Protocol revision history is summarized below.

**Table 1. Protocol Revision Chronology**

Version 1.0	14 May 2021	Original
Version 2.0	29 Jul 2021	Amendment 1
Version 3.0	01 Mar 2022	Amendment 2
Version 4.0	03 Oct 2023	Amendment 3
Version 5.0	02 Oct 2024	Amendment 4

An important consideration in this analysis is that some study subjects may early terminated to enroll in the clinical study, “A Phase 2 Safety, Tolerability, and Proof-of-Concept Study of VGL101 in Patients with Adult-Onset Leukoencephalopathy with Axonal Spheroids Pigmented Glia (ALSP)” (VGL101-01.201), also known as the Ignite study.

## 2 Study Overview

The Illuminate study is a non-interventional, prospective, multicenter, observational, natural history study (NHS) of patients with ALSP and asymptomatic carriers of colony-stimulating factor 1 receptor (CSF1R) gene mutations, the causative mutation for ALSP. Potential study patients will be screened for study eligibility. Individuals who satisfy the study inclusion and exclusion criteria and who provide written informed consent will be enrolled in the study and followed for up to 36 months. Approximately 60 subjects are planned for enrollment. Inclusion and exclusion criteria are detailed in the study protocol.

[figure not shown]
Clinic visits to assess disease status will be conducted at Screening/Baseline and at Months 6, 12, 18, 24, 30, and 36. Each clinic visit will include clinical assessments (cognitive, motor, functional, psychiatric, severity of illness, and caregiver burden assessments) and imaging studies. Blood for biomarker analysis will be collected at Screening/Baseline and at Months 6, 12, 18, 24, 30, and 36. Adverse events (AEs) and concomitant medications and procedures will be recorded throughout the 36-month study.

An optional sub-study to evaluate levels of biomarkers in cerebrospinal fluid (CSF) is also included in this study and will be conducted at select study sites. A CSF sample will be obtained at Screening/Baseline and at Months 6 (Brazil only), 12, 24, 36, and early termination (ET) visits for from subjects who provide informed consent to participate in the optional CSF Biomarker Sub-study. ET visit is mapped in the Electronic Data Capture (EDC) system as the nearest relevant visit in based on days from screening, typically the next subsequent visit.

Subjects who, in the discretion of the investigator, may be eligible for an iluzanebart (VGL101) clinical study may be discontinued from this study at any time. For subjects who discontinue from this study to enroll in an iluzanebart (VGL101) clinical study, all procedures, except the Magnetic Resonance Imaging (MRI), blood biomarker sampling, and CSF collection (for subjects in the CSF Biomarker sub-study), which will be collected once for the ET Visit of this study and for the Screening or Baseline Visit of the iluzanebart (VGL101) clinical study and will be analyzed as part of both studies. If CSF biomarker collection is not included at the Screening or Baseline Visit of the iluzanebart (VGL101) clinical study, CSF biomarker collection will be performed at the ET Visit of this study.

The study schema is presented below, and the Schedule of Assessments is provided in the Appendix (Section 6.1).

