#### **4.1.8 Definition of Baseline**

Unless otherwise specified, for all endpoints, baseline visit is defined as Study Day 1. If the Baseline visit is performed over more than 1 day, then the last day of the baseline assessments will be designated as Study Day 1.

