#### 4.1.10 Study Visit

Scheduled subject visits (i.e., Screening/Baseline, Month 6, Month 12, Month 18, Month 24, Month 30, Month 36) will be determined by the visit as specified in the eCRF. That is, scheduled visits will not be windowed and the nominal visit value will be used for analysis.

To utilize as much data as possible for analysis, unscheduled and ET visits will be mapped to a scheduled visit for analysis using windows as defined below, which are to be used for analysis purposes only. Once analysis visit windows are assigned, all visits, including unscheduled and ET visits, are eligible to be flagged as the “analyzed record” within the analysis window. As such, a subject may have more than one record for each analysis visit window. The following rule for determining which record is flagged as the “analyzed record” is as follows:

- When available, data from the scheduled visit is always used.
- If data from the scheduled visit is not available, then data from the unscheduled or ET visit closest to the scheduled visit study day for that analysis window will be used, if available.

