**Table 2. Study Visit Windows**

Analysis visit	Nominal visit	Analysis visit window (days)		
		Start	End	Target
Baseline	Baseline	-28	1	1
Month 6	Month 6	93	273	183
Month 12	Month 12	275	455	365
Month 18	Month 18	458	638	548
Month 24	Month 24	640	820	730
Month 30	Month 30	823	1003	913
Month 36	Month 36	1006	1186	1096

Unless unscheduled or early termination visits are assigned to a visit window and flagged for analysis, they will be excluded from the summary tables by visit but will be included in the listings.

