#### **4.1.13 Protocol Deviations**

A protocol deviation is any noncompliance with the clinical trial protocol or International Council for Harmonization (ICH) of Technical Requirements for Pharmaceuticals for Human Use Good Clinical Practice (GCP) requirements. The noncompliance may be either on the part of the subject, the investigator, or the study site staff. Protocol deviations will be recorded on the source documents and with an explanation for the deviation. All protocol deviations will also be recorded as specified in the monitoring plan. Protocol deviations will be identified by site staff, through medical reviews, and by clinical research associates during site monitoring.

Deviations will be classified as minor or major prior to the database lock. Major protocol deviations are defined as those that result in harm to the study subjects or significantly affect the scientific value of the reported results of the study. Other deviations will be considered minor.

All protocol deviations will be summarized in a table and well as presented in a listing, including their assigned severity (major/minor). Major protocol deviations will be analyzed separately, and sensitivity analysis may be conducted to assess whether conclusions change when excluding subjects with major deviations. Subgroup analysis may be conducted to evaluate whether protocol deviations disproportionately affect specific subject groups.

Note that visits that occurred outside of visit windows may be identified as a protocol deviation, and these are expected to be relatively common in this study. Some out of window visits may have already been mapped to the appropriate closest visit in the data collection and therefore will not be excluded from the population analysis sets. Protocol deviations due to out of window visits are classified as ‘minor’ unless they occur 90 or more days out of window, in which case they are classified as ‘major.’

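### The SAP has two rules for placing early termination visits and does not say which governs, so an ET assessment could be analysed at a visit due up to about 182 days later

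*SAP*

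**What the plan says.** Two parts of the SAP place an ET record.

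- **Section 2 (Study Overview).** The EDC maps the ET visit "as the nearest relevant visit in based on days from screening, typically the next subsequent visit". The sentence closes the paragraph on the optional CSF sub-study, and its scope is not stated.
- **Section 4.1.10 (Study Visit).** For scheduled visits, "scheduled visits will not be windowed and the nominal visit value will be used for analysis". For the others, "unscheduled and ET visits will be mapped to a scheduled visit for analysis using windows as defined below". Within a window, "When available, data from the scheduled visit is always used"; failing that, the ET or unscheduled record closest to the target day is taken.

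Three further provisions bear on this.

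- **Table 2** gives each analysis visit a start, end and target day; the Month 12 row reads "Month 12 Month 12 275 455 365". The note below it begins "Unless unscheduled or early termination visits are assigned to a visit window and flagged for analysis" and leaves all other such visits to the listings.
- **Section 4.1.8** sets the day count for the windows: if baseline takes more than one day, "the last day of the baseline assessments will be designated as Study Day 1". Section 2 counts from screening. Note b of the Schedule of Assessments allows 28 days for screening and baseline together.
- **Section 4.1.13** adds, on visits outside their window, "Some out of window visits may have already been mapped to the appropriate closest visit in the data collection".

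**The concern.** An ET record that the EDC has stored as Month 12 fits two rules at once. By its label it is a Month 12 visit, analysed as labelled and ahead of other records. By its type it is an ET visit, to be placed by study day. The SAP does not say whether the ET identity survives the EDC mapping or which rule wins, so two programmers could place the same record differently and each cite the SAP. The two rules also count days from different origins, and *nearest* and *next* do not always name the same visit.

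The choice affects outputs that depend on the visit label: the by-visit summaries, the categorical-visit MMRM (Section 4.3.4.1) and the correlations (Section 4.4), where the pairs of primary interest are changes to Month 12. In a disease that worsens, an assessment made early but counted at a later visit tends to make the change at that visit look smaller. ET visits are to be expected, since Section 1 notes that some subjects may leave to enter the Phase 2 study. Untreated change matters because the third study objective is to lay the foundation for an external control arm.

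**Working it through.** There is no figure in the plan to reproduce. The check compares where each rule puts a record, and then illustrates the effect on a mean.

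**Inputs from SAP Table 2.** Targets are days 183, 365, 548, 730, 913 and 1096. Every post-baseline window is its target ±90 days (for Month 12, 365 − 275 = 90 and 455 − 365 = 90). Days 2–92, 274, 456–457, 639, 821–822 and 1004–1005 lie in no window.

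**Two example records** (ignoring the difference in day origin):

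| ET on day | Next visit | Nearest visit | Table 2 |
|---|---|---|---|
| 200 | Month 12, 365 − 200 = 165 days early | Month 6, 200 − 183 = 17 days away | Month 6 (93–273) |
| 380 | Month 18, 548 − 380 = 168 days early | Month 12, 380 − 365 = 15 days away | Month 12 (275–455) |

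In both cases a scheduled record at the Table 2 visit, if there is one, would displace the ET record. *Nearest* and *next* agree only when the ET falls in the second half of an interval.

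**How early a record can be, Month 12.** Take ET days 184 to 364, between the Month 6 and Month 12 targets. Elapsed share is (day − 1)/(365 − 1).

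- Next-visit label: at most 365 − 184 = 181 days early, on average 91. The mean day is 274, so the mean elapsed share is 273/364 = 0.75 and the smallest is 183/364 = 0.50. In the 183-day intervals (Months 18, 30 and 36) the maximum is 182 days.
- Table 2: only days 275 to 364 count toward Month 12, which is 90 of 181 days, or 0.497. These are at most 90 days early, on average 45.5. The mean elapsed share is 318.5/364 = 0.875 and the smallest is 274/364 = 0.75.

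**Illustrative effect on the Month 12 mean change.** These assumptions are not in the documents: change is linear in time, ET days are spread evenly over the interval, all other subjects are seen on target, every ET is labelled next, and a share q of subjects have their ET in this interval.

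- Next-visit label: understatement = q × (1 − 0.75). For q = 0.10 this is 2.5%; for q = 0.30, 7.5%.
- Table 2: understatement = [0.497q / (1 − q + 0.497q)] × (1 − 0.875). For q = 0.10, 0.0497/0.9497 × 0.125 = 0.65%, about 0.7%. For q = 0.30, 0.149/0.849 × 0.125 = 2.2%.

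The part that the label rule adds is therefore about 2.5 − 0.7 = 1.8 to 7.5 − 2.2 = 5.3 percentage points. The same calculation at Month 24 gives 1.3% to 3.7% with next-visit labels and 0.3% to 1.1% with Table 2.

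**Scope.** If the Section 2 sentence concerns only CSF, the visits in question are mainly the annual ones. A next-visit label could then be up to 363 to 365 days early (for Month 12, 365 − 2 = 363), but only for CSF measures.

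**The case against.** The strongest reply is that the analysis rule is already written. Section 4.1.10 windows ET visits, says that the windows serve analysis only, and treats scheduled and ET records as different kinds. Section 2 is then a description of EDC storage. The windowing rule can work only if ET records remain identifiable, and no text says that they do not. This is a fair reading and probably the intended one. It does not settle the matter, because Section 4.1.13 accepts that some labels assigned at data collection carry through to the analysis, and nothing tells the programmer to look behind a scheduled label.

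A reader might go further and infer that ET records do bypass the windows, or that a day-200 ET will be analysed as Month 12. The documents do not support either as fact. Day 200 becomes Month 12 only if *nearest* is ignored, or if *relevant* excludes a Month 6 visit already completed, which the SAP does not say. Applied alone, *nearest* limits the displacement to about half an interval.

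A reader might also take 2.5% to 7.5% as the bias, or ET visits as a main source of data. The number and timing of ETs appear nowhere, so neither follows. The direction is conditional too: if subjects leave because they are declining faster, the effect could be offset or reversed.

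Finally, the study-day MMRM (Section 4.3.4.2) takes its time from actual study day, so its time variable does not depend on the label. How the integrated analysis with the Phase 2 study assigns visits is not in these documents, so a bias in the external-control comparison cannot be asserted from them.

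**Conclusion.** The point holds as a conflict between two placement rules that the SAP should resolve before the analysis is run. It does not hold as a demonstrated understatement of progression. If the EDC label prevails, an ET assessment could be counted up to about 182 days early, against at most 90 under Table 2. The exposed outputs are the by-visit summaries, the categorical-visit MMRM and the visit-based correlations, including those at Month 12.

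The actual size cannot be computed. The percentages for Months 12 and 24 are illustrations that rest on the linear decline, even timing and ET shares assumed above. They also show that windowing reduces the effect but does not remove it. If the Section 2 sentence covers only CSF, the exposure is confined to CSF measures and does not reach the MMRM outcomes of primary interest (ventricle volume, MoCA and CBFS).

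**What to change.** - In Section 4.1.10, state that every ET record, identified by an ET flag whatever its EDC visit label, is assigned to an analysis visit only by actual study day, counted from Study Day 1, using Table 2.
- In Section 2, mark the mapping sentence as EDC storage only and not used for analysis. State whether it covers all ET assessments or only CSF.
- Report how many ET records change visit between the EDC label and the Table 2 assignment. This gives the size that the documents cannot.

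The cost is a few sentences and one programming flag. There is a small loss of data: some ET records will be displaced by a scheduled record (a day-200 ET after a completed Month 6 visit, for example) or will fall between windows, and will appear only in the listings. That runs somewhat against the aim in Section 4.1.10 of using as much data as possible, and the SAP should acknowledge it.

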**Figure 1. Schema for the Illuminate Natural History Study**

a. Attempts will be made to determine the survival status (alive or deceased) of any subject who fails to return for a final visit or who discontinues from the study before completing the 24-month (for subjects who withdraw from the study before implementation of Amendment 3 or 36-month (for subjects who withdraw from the study after implementation of Amendment 3) observation period. Study staff will contact the subject or the subject's caregiver by telephone to determine survival status 24 or 36 months, respectively, after the date of the subject's Screening Visit or at the end of the study, whichever occurs sooner.

### 3 Objectives and Endpoints

#### 3.1 Study Objectives

The Illuminate NHS objectives are as follows:

- To understand the phenotypic heterogeneity and phenotype/genotype correlation and natural history of ALSP.

- To develop and evaluate biomarkers for assessing disease progression in patients with ALSP.
- To create the foundation for a future external control arm and provide run-in data for patients who qualify for interventional studies.

### **3.2 Study Endpoints**

Study endpoints and respective analysis methods are described in [Section 4.3](#).

### **3.3 Analysis Populations and Subgroups**

Analysis populations and subgroups are defined in the following sections.

Hematopoietic Stem Cell Transplant (HSCT) at baseline is used for select analysis population and subgroup criteria. A subject is programmatically determined to have HSCT if there exists any occurrence of “Blood and blood product treatment” or “Haematological therapeutic procedures NEC” in the subject’s Medical History High Level Term (HLT) data.

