8.1 Screening Assessments

8.1.1 *Informed Consent*

The investigator or designated member of the investigational site staff is responsible for providing each subject with adequate explanations of the aims, methods, anticipated benefits, and potential risks of the study and for obtaining written informed consent from each subject (as detailed in [Section 10.1.2](#) before any study-related procedures are performed.

Subjects who meet the criteria for definitive ALSP must have a designated study partner (i.e. caregiver) who spends at least 4 hours per week with them. The study partner must be able and willing to assist the subject in complying with the study requirements, be able to provide information during study visits, and be willing to sign a study partner ICF. Subjects who do not have a study partner may be enrolled at the investigator's discretion if they are able to comply with protocol requirements.

Subjects who meet the criteria for prodromal ALSP and who, at later study visits, meet the criteria for definitive ALSP should have a designated study partner for subsequent study visits who spends at least 4 hours per week with them unless otherwise approved by the sponsor and/or medical monitor. The study partner must be able and willing to assist the subject in complying with the study requirements, be able to provide information during study visits, and be willing to sign a study partner ICF. Subjects who do not have a study partner may continue the study at the investigator's discretion if they are able to comply with protocol requirements.

8.1.2 *Medical/Family History and Demographic Information*

Relevant medical history (including surgical history) will be documented during Screening to assess subject eligibility. Any medical conditions should be captured with at

least a start date and an indication of whether the condition is ongoing or resolved. Detailed information related to family/subject history of ALSP will be recorded.

Date of birth, sex, ethnicity, and race will be recorded.

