8.1.4 Prior and Concomitant Medications/Procedures

All prescription and over-the-counter medications that have been taken during the 30 days before Screening/Baseline through the last study visit will be documented. A complete history of medications taken for the treatment of ALSP will be collected.

Prior medical procedures will also be recorded.

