##### **3.3.1.3 Study Population (Non-HSCT)**

The Study Population (Non-HSCT) consists of all subjects in the Study Population who have not had HSCT procedure. This population includes Prodromal and Symptomatic ALSP subjects.

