#### **4.1.11.2 Imputation of Incomplete Dates**

An incomplete date is any date for which either the day, month or year is unknown, but all three fields are not unknown. An incomplete date occurs when the exact date an event occurred or ended cannot be obtained from a subject. However, a complete date is often necessary to determine if the event should be included in the analysis or to establish the duration of an event. In such cases, incomplete dates will be imputed.

Incomplete or missing start and end dates will be imputed for the following:

- Adverse events
- Medications to determine when the medication was taken (i.e., prior to Baseline or concomitant).
- Procedures to determine when the procedure occurred (i.e., prior to Baseline or concomitant).
- Date of birth will be imputed to determine age at Baseline and age at time of ALSP diagnosis. (Note: if “Birth Date” is incomplete/missing but “Age at Diagnosis of ALSP” is not missing, then the imputed birth date will not be used for the calculation of “Age at Diagnosis of ALSP” and the value recorded in the EDC will be used).
- ALSP diagnosis date will be imputed to determine duration from time of ALSP diagnosis to Baseline.

For the purposes of handling partially reported start and end dates for AEs, medications, procedures, and therapies, the following algorithm will be applied:

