#### **Start Date Imputation Rules**

- **Missing start day, but month and year present:**
  - If the event occurs in the same month and year as Baseline, then the start day of the event will be assigned to the day Baseline (i.e., Day 1).
  - Otherwise, the start day will be set to the first day of the month.
- **Missing start day and month, but year present:**
  - If event occurs the same year as Baseline, then the start date of the event will be assigned to Day 1.
  - Otherwise, the start day and month will be set to 01 January.

- **In the unlikely event of a completely missing start date, the start date will be imputed as Day 1.**
- **If the year and day are present, but month is missing, apply imputation rules as though the day is also missing, and only year is present.**
- **If the imputed start date is after the non-imputed end date, then the start date will be set to the end date.**

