#### **4.2.3 Medical History**

Medical History will be coded using the Medical Dictionary for Regulatory Activities (MedDRA) version 24.0 or higher and summarized for the Study Population. Medical History will be summarized by System Organ Class (SOC) and Preferred Term (PT).

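### Baseline HSCT status rests on two broad Medical History terms that do not name transplant, and the SAP does not require confirmation

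*SAP*

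**What the plan says.** SAP 3.3 makes HSCT at baseline a programmed variable. A subject has "HSCT if there exists any occurrence of “Blood and blood product treatment” or “Haematological therapeutic procedures NEC” in the subject’s Medical History" at the High Level Term level. One matching record is enough. The rule names no Preferred Term or verbatim text and asks for no review of the match.

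The result feeds SAP 3.3.1.3: "The Study Population (Non-HSCT) consists of all subjects in the Study Population who have not had HSCT procedure". It also splits the Symptomatic subgroup in SAP 3.3.2 into Non-HSCT and Prior HSCT.

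More specific data are already available:

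- SAP 4.2.3: "Medical History will be summarized by System Organ Class (SOC) and Preferred Term (PT").
- Protocol 8.1.2: "Relevant medical history (including surgical history) will be documented during Screening to assess subject eligibility".
- Protocol 8.1.4: "Prior medical procedures will also be recorded". SAP 4.2.6 has procedures coded and listed but does not link them to the flag.
- SAP Version History: "BMT and HSCT are interchangeable terms for the purposes of this study", so both names should count as a transplant.

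**The concern.** The two terms are grouping labels. The first describes treatment with blood or blood products, which in ordinary language includes more than transplant. The second ends in NEC, which usually marks a residual group. If either collects a non-transplant record, the subject is classed as transplanted and nothing later in the plan is required to correct it.

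The split has a purpose. Protocol 2.2.4 reports that cognition, motor function and MRI lesions have stabilised for up to 2 years after HSCT, and the rationale for Amendment 3 in the protocol's amendment history treats HSCT as a possible confounder of natural history. The models in SAP 4.3.4 analyse ventricle volume, MoCA and CBFS, which measure related domains. The variable that separates the groups should therefore identify transplant and nothing else, particularly as SAP 4.3.3 foresees using these data as a control group for the Phase 2 study.

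**Working it through.** The plan states no figure that bears on this point, so there is none to reproduce. The check has four parts.

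**1. Does another step correct a false flag?**

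- Independent programming (SAP 4.1.3) checks the code. Two programmers applying the same rule would reach the same false flag.
- Time from HSCT to Baseline (SAP 4.2.2) needs a transplant date, but only for subjects already counted as prior HSCT. An odd or missing value could alert someone, but it does not set or confirm the flag.
- The procedures listing (SAP 4.2.6) could show the truth, but no comparison with the flag is required.

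**2. What does the flag reach?**

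| Output | Effect of one false flag |
|---|---|
| Study Population (Non-HSCT), SAP 3.3.1.3 | subject removed |
| Correlations, SAP 6.3.2 (title read as that population) | subject removed; (8 MRI + 6 fluid) × 4 clinical = 56 endpoint pairs at most, not all at every visit |
| Repeated-measures models, SAP 4.3.4 | 3 endpoints × 2 models = 6; a Symptomatic subject moves between two of the three subgroup levels, a Prodromal subject stays put |
| Baseline, biomarker, clinical and safety subgroup summaries, SAP 4.2.2, 4.3.1, 4.3.2, 4.5 | a Symptomatic subject moves from Non-HSCT to Prior HSCT |
| Correlations of primary interest, SAP 4.4 | none; they use the whole Study Population |

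**3. How large could the effect be?** The documents give no count of transplanted or wrongly flagged subjects, so every count here is an assumption. The formulas are for simple means with equal baselines and visit patterns, not for the planned models.

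- One false flag added to n true Prior HSCT subjects moves that group's mean towards the Non-HSCT mean by 1/(n+1) of the true difference: n = 3, 1/4 = 25.0%; n = 5, 1/6 = 16.7%; n = 10, 1/11 = 9.1%.
- With k true and f false subjects, the true share of the flagged group is k/(k+f): k = 3, f = 3 gives 3/6 = 50%; k = 8, f = 1 gives 8/9 = 89%.
- Losing one of N Symptomatic Non-HSCT subjects at random gives no expected shift and raises the standard error by √(N/(N−1)) − 1: N = 30, 1.7%; N = 40, 1.3%; N = 50, 1.0%.
- A pooled Symptomatic mean weighted by subject counts does not move. With 5 true Prior HSCT subjects at mean 0 and 40 Non-HSCT subjects at mean 1, it is 40/45 = 0.889. After one swap the group means are 1/6 and 1, and (6 × 1/6 + 39 × 1)/45 = 40/45 = 0.889.

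The small Prior HSCT group is the sensitive one.

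**4. A related tension over who can be in that group.** SAP 1 references protocol Version 5.0, and SAP 3.3.1.2 admits to the Study Population only subjects who met the criteria in protocol Section 5. Exclusion 11 in protocol 5.2 names past and planned HSCT and ends with a 12-month limit. If the limit attaches only to planned transplants, any prior HSCT excludes, and the Prior HSCT subgroup in SAP 3.3.2 would be empty. If it attaches to both, the subgroup can have members. The text does not settle which.

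**The case against.** The strongest reply is that no harm can be shown. What falls under a High Level Term depends on the coding dictionary, which the documents do not reproduce, and a group label need not name each procedure it contains. Only relevant history is recorded, and the exclusions remove major illness and most recently treated cancer, so incidental transfusion records may be rare. The sponsor may have chosen these terms after seeing the coded data, although the SAP does not say so. Planned listings could also expose a false flag. This all stands as far as it goes: it limits the point to a risk, but it supplies no required confirmation.

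Three stronger readings are tempting and are not supported:

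- *That the Prior HSCT group is contaminated.* No mislabelled subject appears in the documents.
- *That the lack of a date condition lets in later transplants.* The SAP frames the flag as status at baseline, and the schedules of assessments in both documents place medical history only at Screening/Baseline. That gap is small.
- *That date imputation could shift a transplant across baseline.* The list in SAP 4.1.11.2 includes "Procedures to determine when the procedure occurred (i.e., prior to Baseline or concomitant") but does not include Medical History, which is the source the flag reads.

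It is also fair to object that a narrower rule can miss a true transplant recorded in other words or without a full date, and so place it in the Non-HSCT group. For a natural history reference that may be the worse error. With 60 subjects and an assumed 3 to 8 transplants, missing 1 or 2 would make between 1/58 = 1.7% and 2/54 = 3.7% of the unflagged group transplanted. The remedy has to guard against this.

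**Conclusion.** The point holds as a minor one. The rule relies on labels that do not name transplant, and no step in the plan is required to catch a false match. Misclassification is possible but not shown. Its size cannot be derived, and the figures above rest wholly on assumed counts and simple means.

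A reader might infer that the study's main results are in doubt. They are not: the correlations of primary interest do not use the flag, a count-weighted pooled Symptomatic estimate does not change, and the study is exploratory. What is exposed is the Prior HSCT versus Non-HSCT split in the six models, the subgroup summaries and the second correlation table. The tension between exclusion 11 and the Prior HSCT subgroup is secondary and arises under only one of two readings.

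**What to change.** In SAP 3.3:

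1. Keep the two High Level Terms only as a screen.
2. Set the flag from listed transplant-specific Preferred Terms or verbatim text, covering both haematopoietic stem cell and bone marrow transplant.
3. Cross-check against the recorded prior procedures, so that a transplant worded differently in Medical History is not missed.
4. Confirm every screened-in record by a listing review blinded to outcomes before the database freeze, which SAP 4.1.2 places on or around 11 April 2025.
5. Do not unflag a confirmed prior transplant because its date is missing or partial. Settle its timing in the same review.

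Secondary: reconcile SAP 3.3.1.2, SAP 3.3.2 and exclusion 11 by having 3.3.1.2 refer to the eligibility criteria in force when each subject enrolled.

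The cost is a few lines of SAP text and a short listing review for about 60 subjects, using data already collected and coded. If the two terms already capture only transplants, the review will show it and no result changes.
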